10.2.6.4.1 Recommendations for Elevated CK or CPK

Recommendations for work up of elevated CK or CPK
Please consider other interventions per institution and patients' condition
Repeat level
Blood work: 
 • Comprehensive Metabolic Panel (CMP) • Calcium • Uric Acid
Urine for Myoglobin
EKG
Rule out other causes: 
 • Trauma • Alcohol ingestion • Other medications • Cardiac issues • Central Nervous Systems (CNS Issues)

Treatment (symptomatic or CK level greater than 5,000U/L)

 • Aggressive hydration and diuresis • Admission

10.2.6.5 Treatment Dose Modifications and Guidelines for Reduced Left Ventricular Ejection Fraction Changes

Decreases of the left ventricular ejection fraction (LVEF) have been observed in subjects receiving trametinib. Therefore, ECHO/MUGAs must be performed at screening, at the end of cycle 1, at the end of cycle 3 and then after every 3 cycles thereafter during treatment cycle (e.g. following Cycles 6, 9, and 12). Refer to [Table 6-1 Schedule of Assessments](#) for exact schedule. Any additional or ECHO/MUGAs obtained thereafter should be done only if clinically indicated. The same procedure (either ECHO or MUGA, although ECHO is preferred) should be performed at screening and at follow-up visit(s).

Trametinib Dose Modification Guidelines and Stopping Criteria for LVEF Decrease		
Clinical Manifestations	LVEF-drop (%) or CTCAE grade	Action and Dose Modification
Asymptomatic ^c	Absolute decrease of >10% in LVEF compared to baseline and ejection fraction below the institution's LLN.	
Interrupt treatment and repeat ECHO/MUGA within 2 weeks. ^a
 
 • If the LVEF recovers within 4 weeks (defined as LVEF \geq LLN and absolute decrease \leq 10% compared to baseline): 
 ▪ Consult with the study chair and request approval for restart. ▪ Restart treatment with trametinib at reduced dose. ^b ▪ Repeat ECHO/MUGA 2, 4, 8, and 12 weeks after re-start; continue in intervals of 12 weeks thereafter. • If LVEF does not recover within 4 weeks: 
 ▪ Consult with cardiologist. ▪ Permanently discontinue trametinib. ▪ Report as SAE ▪ Repeat ECHO/MUGA after 2, 4, 8, 12, and 16 weeks or until resolution.
Symptomatic ^{c,d}	
Ejection fraction decreased:
 
 • Grade 3: resting LVEF 39-20% or \geq 20% absolute reduction from baseline • Grade 4: Resting LVEF \leq 20%. 
Left Ventricular Systolic Dysfunction:
 
 • Grade 3: Symptomatic due to drop in ejection fraction responsive to intervention. 	
 • Permanently discontinue trametinib. • Report as SAE. • Consult with cardiologist. • Repeat ECHO/MUGA after 2, 4, 8, 12, and 16 weeks or until resolution.

	
 Grade 4: Refractory or poorly controlled heart failure due to drop in ejection fraction; intervention such as ventricular assist device, intravenous vasopressor support, or heart transplant indicated. 	

^a If ECHO/MUGA does not show LVEF recovery after 2 weeks, repeat ECHO/MUGA 2 weeks later.
 
^b Escalation of trametinib to previous dose level can be considered if LVEF remains stable for 4 weeks after restarting of trametinib. Approval from the study chair is required.
 
^c Symptoms associated with a decreased ejection fraction may include dyspnea, orthopnea, and other signs and symptoms of pulmonary congestion and edema.
 
^d Symptoms associated with a decreased ejection fraction can be graded as per CTCAE v5.0 criteria for Left Ventricular Systolic Dysfunction and/or Ejection fraction decreased.
		

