- iv. Serum albumin may be lowered in this subject population and will not be used to evaluate adequate liver function
- c. Adequate cardiac function as indicated by
 - i. Left Ventricular Shortening fraction of $\geq 27\%$ by echocardiogram **or** ejection fraction of $\geq 50\%$ by MUGA
 - ii. No documented history of congestive heart failure (New York Heart Association functional classification III-IV)
 - iii. No history of long QT syndrome, family history of idiopathic sudden death or congenital long QT syndrome
- d. Adequate Bone Marrow Function
 - i. Hemoglobin ≥ 8 g/dL (may receive RBC transfusions)
 - ii. Absolute Neutrophil Count (ANC) $\geq 750 \times 10^9/L$
 - iii. Platelets $\geq 75 \times 10^9/L$ (independent of transfusions) exception is made for Kaposiform lymphangiomatosis subjects who have a baseline coagulopathy and thrombocytopenia.
- 8. Persons who can get pregnant 11 years of age or persons with early onset menarche must have a negative serum or urine pregnancy test within 7 days prior to the initiation of the study medication.
- 9. Males and females of reproductive potential must agree to the use an acceptable method of contraception, including abstinence, a barrier method (diaphragm or condom), IM progesterone depot, intrauterine contraceptive device, or an oral contraceptive, for the duration of time when they are receiving study drug and for 3 months following last dose.
- 10. Subjects must be able to swallow tablets or liquid or use a nasogastric or gastric tube for liquid study medication administration.
- 11. Subjects who require physiologic or stress doses of steroids due to endocrine deficiencies are eligible.
- 12. Subjects who have previously received MEK inhibitors are eligible if otherwise meeting all eligibility criteria and concomitant medication requirements.

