10.2.1.1 Non-Hematological Dose-Modifying Toxicity

- See [Section 10.2.6](#) for management guidelines for toxicities of special interest. Note that dose modification or discontinuation of trametinib for toxicity is considered a dose modifying toxicity.
- Any Grade 4 non-hematological toxicity with specific exclusion of:
 - Grade 4 fever/pyrexia that resolves to Grade < 2 within 72 hours with supportive care (anti-pyretics)
- Dose-modifying hypertension will be considered as the following:
 - Grade 4 hypertension,
 - A blood pressure > 25 mm Hg above the 95th percentile for age, height, and gender, confirmed by repeated measurement

Note: if elevated, take 3 serial blood pressure readings from the same extremity with the patient in the same position, separated by at least 5 minutes. Avoid using the lower extremity if possible. Use the mean average of the 3 measurements.

- Any Grade 3 non-hematological toxicity with the specific exception of:
 - Grade 3 nausea and vomiting of less < 3 days duration

- Grade 3 fever or infection < 7 days duration.
- Grade 3 hypophosphatemia, hypokalemia, hypocalcemia and/or hypomagnesemia responsive to oral supplementation within 7 days
- Grade 2 allergic reactions that necessitate discontinuation of study drug will not be considered a dose-modifying toxicity
- Any Grade 2 non-hematological toxicity that persists for ≥ 7 days and is considered sufficiently medically significant or sufficiently intolerable by patients that it requires treatment interruption
- Grade 2 left ventricular ejection fraction disease
- Grade 2 cardiac valvular toxicity (mitral/aortic/tricuspid)
- Grade 2 pneumonitis
- Treatment interruption longer than 14 days due to delayed recovery from toxicity will be cause for dose modification

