10.2.3 Dose Modifications for Non-Hematologic Toxicity

If a subject experiences a dose-modifying non-hematologic toxicity as defined in [Section 10.2.1](#), the treatment will be held.

If the toxicity does not resolve to meet inclusion/exclusion parameters or baseline within 14 days of drug discontinuation the subject must be removed from protocol therapy unless specifically documented in toxicities of special interest [Section 10.2.6](#).

If the toxicity resolves to meet inclusion/exclusion parameters or baseline within 14 days of drug discontinuation the subject may resume treatment with a reduction to the next lower dose according to [Appendix II](#). See [Appendix II](#) for dosing modification in subjects receiving oral solution or the specified dose reduction in subjects receiving tablets.

- Doses reduced for toxicity will not be re-escalated, even if there is minimal or no toxicity with the reduced dose, unless otherwise specified in the toxicities of special interest [Section 10.2.6](#).
- If the same dose-modifying toxicity recurs in a subject who has resumed treatment, the subject must be removed from protocol therapy.

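### Two loose ends in the LVEF rules: an asymptomatic fall of at least 20 points with LVEF at or above LLN has no row in 10.2.6.5, and 10.2.1.1 and 10.10 disagree on Grade 2

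*Protocol*

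**What the plan says.** Four parts of the Protocol bear on a fall in LVEF.

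- **10.2.1.1 (what is dose-modifying).** The list includes "Grade 2 left ventricular ejection fraction disease", with no condition on LLN, symptoms or tolerability. Grade 3 non-hematological events are also listed, and LVEF is not among the exceptions. The first bullet points to 10.2.6 "for management guidelines for toxicities of special interest".
- **10.2.3 (what follows).** Treatment is held. Then: "If the toxicity resolves to meet inclusion/exclusion parameters or baseline within 14 days of drug discontinuation the subject may resume treatment", at the next lower dose. If the event has not resolved by 14 days, "the subject must be removed from protocol therapy unless specifically documented in toxicities of special interest". The cardiac eligibility parameter in 5.1 is "Left Ventricular Shortening fraction of" at least 27% on echocardiogram, or an ejection fraction of at least 50% on MUGA.
- **10.2.6.5 (LVEF table).** The asymptomatic row requires "Absolute decrease of >10% in LVEF compared to baseline" together with LVEF below LLN. It leads to interruption, a repeat scan, a 4-week recovery test (at or above LLN and within 10 points of baseline), chair approval to restart, and then "Repeat ECHO/MUGA 2, 4, 8, and 12 weeks after re-start". The symptomatic row, which requires permanent discontinuation, holds the numeric Grade 3 definition: a resting LVEF of 39-20%, or at least a "20% absolute reduction from baseline".
- **10.10 (general schedule).** A tolerable Grade 2 event continues on treatment. An intolerable Grade 2 or a Grade 3 event is interrupted until Grade 0-1 and resumed one level lower.

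**The concern.** LVEF change is a named event of special interest, found largely on scheduled imaging in subjects who may feel well, at 25 sites. Sites need one answer for each finding, and at two points they do not have one.

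For a Grade 2 LVEF event that the subject tolerates, 10.2.1.1 with 10.2.3 stops the drug and 10.10 carries on.

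For a large asymptomatic fall that ends at or above LLN, the specialised table gives no instruction, so the general rules decide the restart. A subject who has lost 20 points could be restarted on a looser cardiac test, and with less planned imaging, than a subject who has lost 11 points and is below LLN. Yet 9.2 counts a Grade 3-4 LVEF decrease toward the toxicity pause rule with no symptom condition, if it is treatment-associated and occurs in the first two courses. The event is treated as serious there but has no management row.

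**Working it through.** There is no plan figure to reproduce. The check sets the rules side by side and works through the cases they leave open.

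**Part (a): tolerable Grade 2 LVEF event attributed to trametinib**

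1. 10.2.1.1: dose-modifying on grade alone, so 10.2.3 holds the drug.
2. 10.10: continue and monitor.
3. Precedence: the exception clauses in 10.2.3 defer to 10.2.6 for the 14-day removal rule and for re-escalation, not for the hold. 10.10 says only that special-interest guidance also exists. No sentence chooses between steps 1 and 2.
4. Against 10.2.6.5: that trigger is a fall of more than 10 points and LVEF below LLN. The Protocol does not print the Grade 2 range, so how often this differs from a Grade 2 trigger cannot be read from the text.

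**Part (b): asymptomatic, fall of at least 20 points, LVEF at or above LLN**

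1. Asymptomatic row: needs LVEF below LLN, so not met. Symptomatic row: needs symptoms, so not met.
2. Baseline required: baseline - current >= 20 and current >= LLN together give baseline >= LLN + 20. The Protocol gives no LLN value. Assuming 50%: 50 + 20 = 70%. Assuming 55%: 55 + 20 = 75%.
3. Worked case on MUGA, LLN assumed 55%, LVEF 75% to 55%:
   - Fall: 75 - 55 = 20, the Protocol's own numeric Grade 3.
   - 55 >= 55, so no row of 10.2.6.5 applies.
   - Hold: yes, under 10.2.1.1/10.2.3 and under 10.10.
   - 10.2.3 eligibility parameter: 55 >= 50, satisfied even at the held value.
   - 10.10: still Grade 3, so Grade 0-1 is not reached.
4. Is this peculiar to one pair of values? Take whole-number baselines from 50% to 80%. With LLN 50%, baselines 70 to 80 give 1 + 2 + ... + 11 = 66 no-row pairs. With LLN 55%, baselines 75 to 80 give 1 + 2 + ... + 6 = 21. In all 66 and all 21, the current LVEF is at least 50% while the fall is still Grade 3. With LLN 45% there are 136 no-row pairs, and the same holds in 66 of them. These are counts of value combinations, not frequencies of patients.
5. On echocardiogram, which 10.2.6.5 prefers, the eligibility parameter is shortening fraction. The 10.2.3 test then need not consult LVEF at all. No number can be worked here, because the Protocol gives no link between the two measures.
6. Imaging after restart: 10.2.6.5 fixes 4 scans in 12 weeks (weeks 2, 4, 8 and 12). On the routine schedule after cycle 3, scans are 3 x 28 = 84 days apart, so 1 fixed scan falls in the same 12 weeks. Extra scans are allowed if clinically indicated.

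**The case against.** The strongest reply is that a specific rule ordinarily overrides a general one. 10.2.1.1 refers special-interest toxicities to 10.2.6, and 10.10 is a table for all adverse events. This has force, but it does not settle either point. The Grade 2 bullet in 10.2.1.1 is itself specific to LVEF, and where 10.2.6.5 has no row there is no specific rule to prevail.

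Several stronger readings are tempting, and the documents do not support them.

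- **That 10.2.3 and 10.10 give opposite orders on restart.** 10.2.3 is permissive and speaks of the toxicity resolving. A clinician could fairly say that an unchanged 20-point fall has not resolved. A site that waits for Grade 0-1 breaches neither resume test. They are a looser and a stricter rule. What stands is that the looser one sets no limit on change from baseline.
- **That the 14-day and 4-week limits conflict.** Where a row of 10.2.6.5 applies, the exception clause in 10.2.3 reconciles them. Where none applies, the 14-day limit is simply the more conservative.
- **That the gap can be sized as a band of LVEF values between the 10.2.3 parameter and the 10.2.6.5 recovery test.** That would compare a rule in force with one that is not triggered, and only for MUGA.
- **That the adult rates in 1.2.2 (about 11% and 5%) size the missing-row case.** Both concern LVEF below LLN, which is the situation this case excludes.
- **That the Grade 3 text of the symptomatic row reaches asymptomatic subjects.** The row label says otherwise. Reading it that way gives permanent discontinuation, a further answer rather than a resolution.

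It also stands that subjects in the missing-row case are not unprotected. They are held, restarted only at a reduced dose, followed to resolution or stabilization under 10.3, and recorded as Grade 3 events.

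**Conclusion.** The point holds in limited form. (a) The Protocol gives two different actions for a tolerable Grade 2 LVEF event, hold under 10.2.1.1/10.2.3 and continue under 10.10, and names no governing rule. The size of any further gap against the 10.2.6.5 trigger is not determinable from the document. (b) An asymptomatic fall of at least 20 points with LVEF at or above LLN has no row in 10.2.6.5. The hold is secure. The restart rests on a test with no limit on change from baseline, alongside a stricter general test, and without the chair approval and fixed re-imaging that the table requires for smaller falls below LLN.

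Case (b) should be uncommon, since it needs a baseline of at least LLN + 20. The 70% and 75% thresholds rest on assumed LLNs of 50% and 55%, and no rate is claimed. This is a minor safety clarification that leaves the endpoints, sample size and error rates untouched.

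**What to change.** 1. Add a row to the 10.2.6.5 table: *Asymptomatic, absolute fall of at least 20 points with LVEF at or above LLN: interrupt; same re-echo, 4-week recovery, chair-approval and post-restart imaging steps as the existing asymptomatic row.*
2. Keep the Grade 2 LVEF bullet in 10.2.1.1, correcting its last word from *disease* to *decrease*.
3. State in 10.10 that its table does not apply to LVEF events: where a row of 10.2.6.5 applies, that row governs; otherwise the hold under 10.2.1.1/10.2.3 applies.

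The Grade 2 bullet should not be replaced by the 10.2.6.5 trigger with that section then made to override everything else. That would remove the present hold for Grade 2 events at or above LLN, and for those below LLN with a fall of 10 points or less.

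The cost is a short protocol amendment (one row, one word, one precedence statement) and a few extra echocardiograms in the few subjects who are restarted.

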10.2.6.6 Treatment Dose Modifications and Guidelines for Pneumonitis

Pneumonitis has been observed in subjects receiving trametinib. To reduce the risk of pneumonitis, subjects will be monitored closely for symptoms and evaluated with routine physical examination and pulse oximetry measurements done as part of routine vitals. Additional imaging to include CXR, CT scan or PFTs if there is clinical concern for pneumonitis. Dose modification and supportive care guidelines for pneumonitis are described in the tables below.

Dose Modification for Pneumonitis

Pneumonitis (NCI CTCAE v5.0)	Recommended Management Guidelines	Dose Modification Requirement
Grade 1	
CT scan (high-resolution with lung windows) recommended, with serial imaging to monitor for resolution or progression – re-image at least every 3 weeks.
 
 Monitor for symptoms every 2-3 days – Clinical evaluation and laboratory work-up for infection. Monitoring of oxygenation via pulse oximetry recommended. Consultation of pulmonologist recommended. 	Continue treatment at the same dose level.

Grade 2	
CT scan (high-resolution with lung windows)
 
 Monitor for symptoms daily, consider hospitalization Clinical evaluation and laboratory work up for infection Consult pulmonology Pulmonary function tests- if normal at screening, repeat every 8 weeks Bronchoscopy with biopsy and/or BAL recommended Symptomatic therapy including corticosteroids if clinically indicated (systemic corticosteroids at dose of 1 to 2 mg/kg/day prednisone or equivalent as clinically indicated). 	
1st occurrence:
 
 Interrupt treatment until recovery to \leq Grade 1 or baseline. Once recovered, dose reduce as per Section 10.2.3^a If no recovery to \leq Grade 1 within 4 weeks, permanently discontinue treatment. If worsens treat as Grade 3 or 4.
Grade 3	
CT scan (high-resolution with lung windows)
 
 Clinical evaluation and laboratory work-up for infection Consult pulmonologist PFTs- if $<$ normal, repeat every 8 weeks until normal Bronchoscopy with biopsy and/or BAL if possible Treat with intravenous steroids as indicated. When symptoms improve to \leq Grade 1, a high dose oral steroid (prednisone 1 to 2 mg/kg once per day or dexamethasone 4 mg every 4 hours or equivalent). If IV steroids followed by high dose oral steroids does not reduce initial symptoms within 48 to 72 hours, consider non-corticosteroid immunosuppressive medication. 	
Interrupt treatment until recovery to Grade \leq 1 or baseline.
 
 Once recovered, dose reduce as per Section 10.2.3^a 
If no recovery to Grade \leq 1 or baseline within 4 weeks, permanently discontinue treatment.

Grade 4	Same as Grade 3.	Same as Grade 3

^a Escalation of trametinib to previous dose level can be considered if no recurrence of pneumonitis for 4 weeks after restarting of trametinib. Approval from the study chair is required.

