4 INVESTIGATIONAL PLAN

4.1 General Schema of Study Design

This study is a single-arm, open-label investigational Phase II study of trametinib administered orally or by naso- or gastric-tube on a continuous 28-day cycle, for up to 24 cycles in subjects ages 2 months to 30 years with genetically confirmed Ras/MAPK pathway

associated vascular or complex lymphatic anomalies. Subjects in the absence of toxicity and with clinical benefit may continue into the extension period for 36 cycles total.

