4.3.1 Dosing

Eligible subjects will be treated with trametinib administered at 0.025 mg/kg/dose (or 0.0125mg/kg/dose for critically ill subjects, infants < 10kg at enrollment, or based on clinical discretion) daily given orally by tablet or by oral solution via a nasogastric tube (NGT) or gastric tube (GT) at dose level 1 for each disease strata. Dosing will be daily on a continuous 28-day cycle, for up to 24 total cycles. Dosing will be based on weight in kilograms (kg) obtained within 7 days of starting each cycle or pre-determined dosing weight in those subjects whom fluid status fluctuates. The total daily trametinib dose should not exceed the adult dose (2mg) in any subject.

Refer to [Section 10](#) for dose modifications for toxicity.

Trametinib formulations include:

Powder for oral solution: The liquid concentration is 0.05 mg/mL. Doses of trametinib oral solution will be rounded to nearest 0.1mL (0.005 mg) for doses ≤ 0.11 mg (in oral syringes ≤ 3 mL), 0.2 mL (0.01mg) for doses > 0.11 mg (in oral syringes of 5-10 mL volume). Trametinib pediatric oral solution formulation will be administered with a graduated syringe.

Tablet formulation: Doses of tablet formulation should be rounded to the nearest 0.5mg. It is recommended that subjects drink 4 to 6 mL of water/kg body weight following dosing.

A dosing nomogram ([see Appendix II](#)) based on weight and dose level will be used to prescribe trametinib to minimize inter-subject dosing variability. If vomiting occurs after taking the oral solution formulation, the dose should not be repeated, and next dose given at its scheduled time.

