10.2.6.3 Reactive Treatment of Dermatologic Toxicity (Rash)

This is meant to be in supplement to prophylactic measures undertaken per Section [10.1.6.2](#).

Rash Management (Reactive/Symptomatic) Recommendations Table
--

Subject Group	Prepubescent Subjects		Postpubescent Subjects
Mild Rash	Dermatitis 
 • Add Hydrocortisone 2.5% cream/ointment BID to affected face and skinfolds, consider escalation to Triamcinolone 0.1% ointment on trunk and extremities 	Acneiform Rash 
 • Add Clindamycin lotion 1% BID if not already in use. • Hydrocortisone 2.5% cream/ointment BID can also be added 	Acneiform Rash 
 • Add Clindamycin lotion 1% BID if not already in use. • Hydrocortisone 2.5% cream/ointment BID can also be added, consider escalation to triamcinolone 0.1% ointment
Moderate to Severe Rash	Dermatitis 
 • Add Hydrocortisone 2.5% cream/ointment BID to affected face and skinfolds, consider escalation to Triamcinolone 0.1% ointment on trunk and extremities 	Acneiform Rash 
 • In addition to above systemic antibiotics with: Cephalexin 20mg/kg/day divided BID (with max dose of 500 mg) for up to 6 weeks OR Amoxicillin 25 mg/kg/day divided BID (with max dose of 875 mg) for up to 6 weeks 	
 • Add systemic antibiotic with a tetracycline (e.g. doxycycline or minocycline) for 3 months
Dermatology referral	Dermatitis which is uncontrolled with recommended supportive care or requiring escalation recommend referral to Dermatology. Additional management may include stronger potency topical steroids, additional antibiotics, or oral retinoids.		

Skin toxicity in the form of rash, fissuring, desquamation, or paronychia is a frequent adverse event (AE) in subjects treated with trametinib. We will use the following management, including dose modification.

CTCAE Grade	Adverse Event Management	Action and Dose Modification
Grade 1	Initiate prophylactic and reactive/symptomatic treatment measures Reassess after 2 weeks	Continue treatment If rash does not recover to baseline within 2 weeks despite best supportive care, dose reduction to the next lower dose as per Appendix II .

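### Steroid guidance for Grade 3 and 4 pneumonitis offers a flat 24 mg/day of dexamethasone, with no weight or age limit, in a trial open to infants under 10 kg

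*Protocol*

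**What the plan says.** The pneumonitis table in Protocol section 10.2.6.6 has a column headed "Recommended Management Guidelines" and a separate column of required trametinib dose modifications. The steroid advice sits in the first.

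- **Grade 2:** "systemic corticosteroids at dose of 1 to 2 mg/kg/day prednisone or equivalent as clinically indicated". This is weight-based only.
- **Grade 3:** intravenous steroids as indicated, then, once symptoms have improved to Grade 1 or less, an oral step-down: "prednisone 1 to 2 mg/kg once per day or dexamethasone 4 mg every 4 hours or equivalent".
- **Grade 4:** "Same as Grade 3".

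Section 4.1 describes treatment "in subjects ages 2 months to 30 years". Section 4.3.1 allows a reduced trametinib starting dose for "infants < 10kg at enrollment". The lowest weight row in Appendix II is 9.0 to 9.9 kg, and the highest begins at 70.1 kg.

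**The concern.** The Grade 3 row presents two oral regimens as alternatives. One is dosed per kilogram; the other is the same at every weight. Nothing in that section or elsewhere in the protocol confines the flat dose to adults or to a minimum weight.

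It also departs from how the protocol handles comparable drugs where it prints a dose. The Grade 2 row of the same table scales the steroid by weight. The rash table in section 10.2.6.3 doses oral antibiotics for prepubescent subjects per kilogram with a maximum, for example "Cephalexin 20mg/kg/day divided BID (with max dose of 500 mg) for up to 6 weeks". Section 10.2.6.7 bands loperamide by age and weight.

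What is at stake is participant safety. A clinician who used the dexamethasone option for an infant or small child would give far more steroid than the option printed beside it. Pneumonitis is a listed event of special interest (section 10.2.6), so the protocol foresees that this guidance may be used.

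**Working it through.** The protocol states no daily total or equivalence for the two steroids, so there is no planned figure to reproduce. The check is arithmetic on the printed doses.

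**Inputs**
- Dexamethasone: 4 mg every 4 hours, flat (section 10.2.6.6, Grade 3).
- Prednisone: 1 to 2 mg/kg once daily (same sentence).
- Weights: 9.0 kg and 70.1 kg from Appendix II; 10 kg from section 4.3.1; 70 kg as a round adult weight. A weight of 5 kg is assumed, to represent an infant near the lower age limit; Appendix II has no row that low.
- Potency of dexamethasone per milligram relative to prednisone, *p*: not in the documents. Assumed range 4 to 7.5.

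**Step 1. Daily dose.** 4 mg × (24 h ÷ 4 h) = 4 × 6 = 24 mg/day at every weight. Prednisone at weight *w* kg is *w* to 2*w* mg/day.

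**Step 2. Ratio of the two options.** In milligrams, the ratio runs from 24/(2*w*), against 2 mg/kg, to 24/*w*, against 1 mg/kg. The last column multiplies the low end by 4 and the high end by 7.5.

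| Weight (kg) | Prednisone (mg/day) | Milligram ratio | Ratio with *p* = 4 to 7.5 |
|---|---|---|---|
| 5 (assumed) | 5–10 | 2.4–4.8 | 9.6–36 |
| 9 | 9–18 | 1.3–2.7 | 5.3–20 |
| 10 | 10–20 | 1.2–2.4 | 4.8–18 |
| 12 | 12–24 | 1.0–2.0 | 4.0–15 |
| 70 | 70–140 | 0.17–0.34 | 0.7–2.6 |

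The milligram column is the same as setting *p* = 1. On that basis 24 mg exceeds the top of the prednisone range whenever 2*w* < 24, that is, below 12 kg. If dexamethasone is the more potent drug per milligram, this column understates the gap.

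Measured only against the upper prednisone dose of 2 mg/kg, the range at 10 kg is 1.2 × 4 = 4.8 to 1.2 × 7.5 = 9.0.

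**Step 3. Where the options agree, for any potency.** The flat dose is worth 24*p* mg of prednisone. It lies within 1 to 2 mg/kg when *w* ≤ 24*p* ≤ 2*w*, that is, when 12*p* ≤ *w* ≤ 24*p*. The window is always two-fold in weight:
- *p* = 1: 12 to 24 kg
- *p* = 4: 48 to 96 kg
- *p* = 7.5: 90 to 180 kg

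Appendix II spans 70.1 ÷ 9.0 = 7.8-fold before counting anyone heavier or lighter. No potency ratio makes the two options equivalent across the trial population. Anywhere in the assumed range of *p*, the flat dose exceeds the whole prednisone range for every subject below 12 × 4 = 48 kg.

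**The case against.** The strongest reply is that no one is required to receive this dose. The column is advisory, a pulmonologist is consulted, intravenous steroids come first, prednisone per kilogram is listed first, the wording allows an equivalent, and section 7.4 leaves supportive care to the provider. Harm needs a clinician to pass over the weight-based option and give a flat dose to a small child who has had Grade 3 or 4 pneumonitis. The protocol gives no expected number of such children, and the event may be rare. All of that stands and lowers the practical risk. It does not make the printed dose correct for those to whom it could be applied.

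A second reply is that the large multiples depend on a potency ratio found nowhere in the protocol, and that the 36-fold figure combines an assumed weight, the highest potency and the lowest prednisone dose. This is fair as to size: that figure is an extreme. The two-fold window in step 3 holds for every potency, so the conclusion does not depend on the ratio chosen.

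Third, the protocol's supportive-care dosing is mixed. The rash table mentions oral methylprednisolone without a dose, and loperamide may follow institutional guidelines. That weakens any claim of a uniform convention, but leaving a dose to local practice differs from printing one that does not fit children.

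**Conclusion.** The concern holds. The Grade 3 and 4 rows print a steroid dose that would be wrong for a small child if followed, and they present it as an alternative to a weight-based dose it cannot match across the trial's weight range.

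From the protocol alone: 24 mg/day at every weight, agreement with 1 to 2 mg/kg over at most a two-fold span of weight, and a milligram excess over the top of the prednisone range below 12 kg. On the assumed potency of 4 to 7.5, the excess is 4.8- to 18-fold at 10 kg, against 0.7- to 2.6-fold at 70 kg.

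The issue is confined to supportive-care text. It should be corrected for participant safety. It does not touch the efficacy test, the power or error rates, or the toxicity stopping boundary in section 9.2.

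**What to change.** Remove the flat dexamethasone option, so that the Grade 3 row, and Grade 4 through it, gives prednisone at 1 to 2 mg/kg/day or equivalent, in line with Grade 2.

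If dexamethasone is to stay, express it as a weight-based equivalent with a maximum daily dose, and restrict 4 mg every 4 hours to subjects of adult weight. The prednisone dose is also uncapped in both rows (140 mg/day at 70 kg and 2 mg/kg), so the clinical lead should decide at the same time whether to add a maximum there. The sponsor's clinical lead and pharmacist should set the exact doses.

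The cost is an amendment to one table cell, or two if a prednisone cap is added to both rows. Data collection, sample size and analysis are unchanged.
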